# The Study Design

## **Title**

The safety and efficacy of irreversible electroporation versus standard medication for the treatment of benign prostatic obstruction: a randomized controlled trial

## **Aims**

Aim: To investigate the safety and feasibility of irreversible electroporation for patients with benign prostatic obstruction.

## **Inclusion Criteria**

[figure not shown]
1. Male, 45 years or older.
2. The presence of voiding symptoms, i.e. slow stream, intermittent stream, hesitancy, straining, etc.
3.  $Q_{\max} \geq 5$  mL/s and  $\leq 15$  mL/s with minimum voided volume of 125 mL or more during flow study.
4. The presence of bladder outlet obstruction during pressure-flow study.
5. International Prostatic Symptom Score (IPSS)  $\geq 12$  at screening.
6. Prostate volume  $\geq 30$  ml (using a transrectal ultrasound approach).
7. Total serum prostatic specific antigen (PSA)  $\geq 1.5$  ng/mL and  $\leq 10$  ng/mL at screening.
8. Subject is able to communicate and complete the questionnaires properly.
9. Written informed consent.

## **Exclusion Criteria**

1. Diagnosis or suspicion of bladder, prostate, urethral or pelvic tumor.
2. Patients with arrhythmia or history of cardiac pacemaker implantation.
3. Known lower urinary tract or pelvic surgical history.
4. Voiding symptoms as a result of urethral stricture, stone diseases, chronic prostatitis, space-occupying lesions etc.
5. Known neurogenic or congenital lower urinary tract dysfunction.

6. Rigid or flexible cystoscopy examination within the past 7 days at screening.
7. Existence of anatomical abnormalities of the urinary tract (e.g. diverticulum of the bladder or urethra, ectopic ureteral orifice etc.).
8. The presence of acute conditions, such as, urinary tract infection, fever, heart failure etc.
9. Patients with poor compliance or cognitive competence.

### **Study design flow diagram**

### **Primary Outcomes**

1. The changes of maximum flow rate (ml/s) between baseline and during follow-up: Maximum flow rate will be measured using urinary flow study. Measured at baseline and 1, 3, 6 months during follow-up.

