### **Secondary Outcomes**

1. The changes of IPSS scores between baseline and during follow-up: Measured using a standard IPSS scoring system. Measured at baseline and 1, 3, 6 months during follow-up.
2. The changes of IIEF scores between baseline and during follow-up: Measured using a standard IIEF scoring system. Measured at baseline and 1, 3, 6 months during follow-up.
3. The changes of maximum detrusor pressure at maximum flow rate between baseline and during follow-up: The data will be captured during pressure flow study. Measured at baseline and 3, 6 months during follow-up.
4. The changes of post void residual volume (ml) between baseline and follow-up: post void residual volume (ml) will be measured via ultrasound. Measured at baseline and 1, 3, 6 months during follow-up.
5. The changes of prostate volume (ml) between baseline and follow-up: Prostate volume (ml) will be measured using transrectal prostate ultrasound and calculated as: prostate volume (ml) = length (mm) \* width (mm) \* height (mm) \* 0.52. Measured at baseline and 1, 3, 6 during follow-up.
6. The documentation of IRE procedure and medication related side effects. Measured at baseline and 1, 3, 6 months during follow-up.

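### Must the 125 mL voided-volume condition at entry be written into the primary outcome for the flow studies at 1, 3 and 6 months?

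*Protocol*

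**What the plan says.** The volume condition appears once, in Inclusion Criteria item 3. A man qualifies with a Qmax between 5 and 15 mL/s, "with minimum voided volume of 125 mL or more during flow study". The item names no visit, whereas items 5 and 7 (IPSS and PSA) are tied to screening.

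Primary Outcomes item 1 is the only primary outcome: "The changes of maximum flow rate (ml/s) between baseline and during follow-up". On method and timing it says: "Maximum flow rate will be measured using urinary flow study. Measured at baseline and 1, 3, 6 months during follow-up". It gives no minimum volume and no instruction for a small void. Baseline is not defined anywhere in the protocol, and voided volume is not listed among the outcomes.

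Prostate volume is the nearest parallel. Inclusion item 6 requires it to be taken "using a transrectal ultrasound approach", and Secondary Outcomes item 5 repeats the method: "Prostate volume (ml) will be measured using transrectal prostate ultrasound".

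**The concern.** The protocol itself treats a Qmax from a small void as not good enough for entry. If the entry flow is also the baseline, and follow-up flows are accepted at any volume, then each patient's change subtracts a value taken under a floor from one taken without it. If smaller voids give lower flows, which is assumed here, the follow-up mean is pulled down and the improvement within each arm is understated. If small voids are also more frequent in one arm, the comparison between irreversible electroporation and medication moves too.

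There is a practical edge as well. Two sites could both follow the text and act differently on a 90 mL void: one repeats the flow, the other records it. A repeat that was not done, or a volume that was not written down, cannot be recovered by a later analysis plan.

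**Working it through.** The protocol states no sample size, SD, effect size or voided-volume figure, so there is nothing of its own to reproduce. Only two inputs come from the document: the 125 mL cut-off and the 5 to 15 mL/s window. All others below are assumptions chosen to show a range.

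**1. Within-arm effect of having no floor at follow-up.** Let voided volume V be lognormal with median 200 mL and CV 0.45, and let Qmax = Q200 × (V/200)^b, with Q200 (Qmax at 200 mL) of 12 or 15 mL/s and b from 0.3 to 0.5.

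- Log-SD = √ln(1 + 0.45²) = 0.429.
- z = ln(125/200)/0.429 = −1.09, so 13.7% of voids fall below 125 mL.
- Understatement = E[Q | V ≥ 125] − E[Q] = share of low voids × mean deficit of a low void.
- Smallest case (b = 0.3, Q200 = 12): 0.137 × 2.69 = 0.37 mL/s. Largest case (b = 0.5, Q200 = 15): 0.137 × 5.41 = 0.74 mL/s.

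| Median volume, CV | Below 125 mL | Understatement (mL/s) |
|---|---|---|
| 250 mL, 0.45 | 5.3% | 0.17–0.35 |
| 200 mL, 0.35 | 8.3% | 0.19–0.38 |
| 200 mL, 0.45 | 13.7% | 0.37–0.74 |
| 200 mL, 0.55 | 18.0% | 0.56–1.13 |
| 150 mL, 0.45 | 33.6% | 0.76–1.49 |
| any, if b = 0 | – | 0 |

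**2. The opposing effect under the same premise.** If the qualifying flow is reused as baseline, selection on 5 to 15 mL/s brings regression to the mean. With normal Qmax among screened men and test-retest reliability r, the expected shift without any treatment effect is (1 − r) × (screened mean − mean of those who qualify).

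- Screened mean 10, the centre of the window: 0.
- Screened mean 12, SD 5, r = 0.6: 0.4 × (12 − 10.58) = +0.57 mL/s.
- Screened mean 14, SD 5, r = 0.6: 0.4 × (14 − 11.13) = +1.15 mL/s.

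Over means of 12 and 14, SDs of 4 and 5 and reliabilities of 0.6 to 0.9, the shift runs from +0.12 to +1.15 mL/s. Setting this roughly against the central case in step 1, the net within-arm error lies between 0 − 0.74 = −0.74 and 1.15 − 0.37 = +0.78 mL/s. Its sign is not determined.

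**3. The randomized contrast.** Regression to the mean is expected to be equal in both arms and cancels. For low voids, with the same deficit in both arms, the bias is the difference in share × deficit.

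- Equal shares: 0.
- A 10-point difference in share: 0.10 × 2.69 to 0.10 × 5.41, or about 0.3 to 0.5 mL/s.
- Equal shares but Q200 of 15 in one arm and 12 in the other: the arm difference of about 3 mL/s shrinks by 0.46 − 0.37 = 0.09 (b = 0.3) to 0.74 − 0.59 = 0.15 (b = 0.5).

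**4. What a floor would gain.** Suppose the whole volume distribution differs, with medians of 180 and 220 mL. The volume-driven contrast is 0.73–1.54 mL/s without a floor and 0.51–1.11 with one, so 69–72% remains. With medians of 150 and 200 mL it is 1.00–2.06 against 0.61–1.31, and 61–64% remains. If low flows are repeated at the visit and the failures kept, a 30% success rate leaves 0.70 × 0.37 to 0.70 × 0.74 = 0.26–0.52 mL/s of the understatement in step 1. A 70% rate leaves 0.11–0.22.

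**5. The prostate-volume parallel.** What Secondary Outcomes item 5 repeats from entry is the method. Qmax is treated alike, since a flow study is named in Inclusion item 3 and again in Primary Outcomes item 1. No outcome restates a per-test minimum, so the protocol is not inconsistent with its own practice.

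**The case for a change.** The best case for a change is that repeating a flow and recording its volume happen at the visit. A statistical analysis plan can define baseline and can exclude, flag or adjust for small voids, but only if the volumes are there. Writing the condition into the primary outcome would take a few sentences and one data field.

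Part of this stands. The protocol does leave the follow-up condition open, and it is fair to ask the investigators which reading they follow. But the protocol does not say that volume goes unrecorded. Criterion 3 can be applied only if the flow study yields the volume, and the same test is used at follow-up. With volume at hand, low flows can be identified in the analysis whatever the sites did about repeats.

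Nor is a floor with repeats clearly the better rule. It is one choice among several and, by step 4, leaves most of a volume-driven difference between arms in place. If treatment itself alters voided volume, part of that difference is a treatment effect that a floor would remove.

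**Conclusion.** No change to the plan is needed. The protocol is silent on whether the 125 mL condition carries over to follow-up; it neither drops nor contradicts it. Applying the entry standard to the same test later is the natural reading, and the choice of baseline value is ordinary content for an analysis plan that may exist but is not shown.

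Under the assumed inputs the within-arm understatement could be anything from 0 to about 1.5 mL/s. Regression to the mean offsets it by 0 to about 1.2 mL/s if the qualifying flow is the baseline, so no direction can be claimed. The comparison that randomization protects is unbiased when low-volume voids are equally common and equally deficient in the two arms. It shrinks by about 0.1 mL/s if they are equally common but the arms differ by 3 mL/s. A larger distortion, 0.3 to 0.5 mL/s per 10 percentage points, requires an imbalance that nothing in the protocol shows. The conclusion assumes that voided volume is kept with each flow, as the entry criterion already requires once.

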### **Secondary Outcomes**

1. The changes of IPSS scores between baseline and during follow-up: Measured using a standard IPSS scoring system. Measured at baseline and 1, 3, 6 months during follow-up.
2. The changes of IIEF scores between baseline and during follow-up: Measured using a standard IIEF scoring system. Measured at baseline and 1, 3, 6 months during follow-up.
3. The changes of maximum detrusor pressure at maximum flow rate between baseline and during follow-up: The data will be captured during pressure flow study. Measured at baseline and 3, 6 months during follow-up.
4. The changes of post void residual volume (ml) between baseline and follow-up: post void residual volume (ml) will be measured via ultrasound. Measured at baseline and 1, 3, 6 months during follow-up.
5. The changes of prostate volume (ml) between baseline and follow-up: Prostate volume (ml) will be measured using transrectal prostate ultrasound and calculated as: prostate volume (ml) = length (mm) \* width (mm) \* height (mm) \* 0.52. Measured at baseline and 1, 3, 6 during follow-up.
6. The documentation of IRE procedure and medication related side effects. Measured at baseline and 1, 3, 6 months during follow-up.

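### The prostate volume formula in secondary outcome 5 multiplies millimetres but labels the result ml, so absolute volumes and changes calculated as written are 1000 times too large

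*Protocol*

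**What the plan says.** Item 5 of the protocol's Secondary Outcomes names the endpoint as "The changes of prostate volume (ml) between baseline and follow-up". It then gives the derivation: "Prostate volume (ml) will be measured using transrectal prostate ultrasound and calculated as: prostate volume (ml) = length (mm"), multiplied by "width (mm) \* height (mm) \* 0.52". The formula stops at 0.52, and the next words are the visit schedule: "0.52. Measured at baseline and 1, 3, 6 during follow-up".

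Two other places give context:

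- Inclusion criterion 6 sets a lower limit of 30 on prostate volume, in "ml (using a transrectal ultrasound approach"). The unit and imaging route are those of item 5, but no formula is cited.
- The primary outcome is obtained by a different measurement: "Maximum flow rate will be measured using urinary flow study".

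This is the only volume formula in the protocol.

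**The concern.** The two sides of the equation are in different units. The left side is in ml. The right side is a product of three lengths in mm and a constant, which is a quantity in cubic millimetres. Unless the constant contains the conversion, the equation cannot be right for any gland.

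What is at stake is the absolute scale of a named secondary outcome, measured at baseline and at three follow-up visits. Because the endpoint is a change expressed in ml, both the volumes and their changes would be mis-scaled.

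A further risk is inconsistency. If some volumes were read directly in ml from the ultrasound equipment and others were built from mm dimensions with the protocol's formula, the dataset would mix two scales, and a mixture, unlike a uniform factor, would distort comparisons. The protocol does not say whether this would happen, so it is a risk and not an established fact.

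**Working it through.** **Inputs from the protocol.** Item 5 of Secondary Outcomes gives the output unit (ml), the unit of all three dimensions (mm) and the coefficient (0.52). Inclusion criterion 6 gives a threshold of 30 ml. The protocol contains no worked volume, so there is no stated figure to reproduce. The gland dimensions below are assumptions chosen for illustration; the factor of 1000 does not depend on them.

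**Step 1: units.** 1 ml = 1 cm³ = (10 mm)³ = 1000 mm³. Hence mm × mm × mm × 0.52 is in mm³, and the value in ml is that result divided by 1000.

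**Step 2: does the coefficient hide the conversion?** The volume of an ellipsoid with diameters L, W and H is (π/6) × L × W × H, and π/6 = 0.5236. The protocol's 0.52 is this number rounded, so it is dimensionless. A coefficient that also converted mm³ to ml would be 0.52 / 1000 = 0.00052.

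**Step 3: the formula as written and corrected.**

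| Assumed dimensions (mm) | As written, labelled ml | Divided by 1000, or dimensions in cm |
|---|---|---|
| Example A, baseline: 50 × 40 × 30 | 60,000 × 0.52 = 31,200 | 5.0 × 4.0 × 3.0 × 0.52 = 31.2 ml |
| Example A, follow-up: 45 × 36 × 27 | 43,740 × 0.52 = 22,744.8 | 4.5 × 3.6 × 2.7 × 0.52 = 22.7 ml |
| Example A, change | −8,455.2 | −8.5 ml |
| Example B, baseline: 40 × 50 × 50 | 100,000 × 0.52 = 52,000 | 52.0 ml |
| Example B, follow-up: 36 × 46 × 46 | 76,176 × 0.52 = 39,611.5 | 39.6 ml |
| Example B, change | −12,388.5 | −12.4 ml |

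The ratio between the last two columns is 1000 throughout, apart from rounding.

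**Step 4: what does not change.** The percentage change in example A is −8,455.2 / 31,200 = −27.1%, and −8.4552 / 31.2 = −27.1%. In example B it is −23.8% on either scale. For a between-group test, multiplying every observation by 1000 multiplies the mean difference and its standard error by 1000, so their ratio, the t statistic, is unchanged.

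**Step 5: scale check against inclusion criterion 6.** Assume equal sides. A true 30 ml gland then has sides of (30,000 / 0.52)^(1/3) = 38.6 mm, and item 5 as written would record it as about 30,000 ml. Conversely, the formula as written returns 30 when the sides are (30 / 0.52)^(1/3) = 3.9 mm. If item 5 were applied literally at screening, the threshold would exclude practically nobody. Criterion 6 does not refer to item 5, so this consequence is conditional only.

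**The case against.** The best argument against giving this much weight is that the error exposes itself. A prostate recorded as 31,200 ml, about 31 litres, is impossible, and the 30 ml in inclusion criterion 6 shows the scale intended. Whoever calculated the first volume would probably notice. A uniform factor of 1000 is fully reversible, changes no test or percentage change, and does not touch the primary outcome. The screening consequence requires an application of the formula that the protocol nowhere states.

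All of this is fair as a limit on importance, and it keeps the point well short of a threat to the trial's main conclusion. It does not make the equation right. The protocol states a rule for deriving an outcome, and that rule gives wrong absolute values when followed. Anyone who repairs it silently departs from the written definition.

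Two other defences fail. The unit mm appears on all three dimensions, so a misreading of the PDF is unlikely. A statistical analysis plan that is not at hand does not excuse a formula the protocol itself states wrongly.

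The missing word months in item 5 is a separate slip. The primary outcome and the other five secondary items all state it, so the meaning is not in doubt and it carries no weight here.

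**Conclusion.** The concern holds. As written, the formula returns cubic millimetres under the label ml, so absolute prostate volumes and absolute changes are overstated by exactly 1000. That conclusion rests only on the definition of the ml and on 0.52 being a shape factor. The assumed gland sizes serve as illustration and nothing more.

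The consequence is confined to the absolute values of one secondary outcome. An effect on comparisons would require volumes from different sources to be mixed, and an effect on eligibility would require literal use of the formula at screening; the protocol states neither. The formula should be corrected, but it is not a flaw in the design.

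**What to change.** In Secondary Outcomes item 5, use one of two equivalent forms:

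- volume in ml = length × width × height × 0.52, with all three dimensions in cm; or
- volume in ml = length × width × height × 0.52 / 1000, with all three dimensions in mm.

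It would also help to state that one calculation applies at all visits and to the screening volume in inclusion criterion 6, so that every volume is on one scale. This is a clarification beyond the necessary correction, and the threshold itself stays as it is. Add months to the visit times in item 5 in the same edit.

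The cost is a short text correction to the protocol, with no effect on the design, the sample or the visits. Any volumes already derived with the formula as written need only be identified and divided by 1000.

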### **Detailed Description**

Benign prostatic obstruction (BPO) is the main reason to cause lower urinary tract symptoms (LUTS) in aged male. Oral medications, such as,  $\alpha$  1-adrenoceptor antagonist and 5  $\alpha$  -reductase inhibitors are the mainstay treatment options. However, some patients can not tolerate long-term use, due to either side effects or limited efficacy. Though transurethral resection or enucleation of prostate usually achieve significant symptom improvement, it's an end stage procedure and it is only reserved for carefully selected patients.

The development of focal ablative therapy yields minimally invasive treatment option for primary tumors such as the liver, lung, pancreas, kidney, and prostate. Among the novel techniques are cryoablation, radiofrequency ablation (RFA), microwave ablation, and high-intensity focused ultrasonography. Irreversible electroporation (IRE) is a one of the ablation modalities using electric pulses to create nanoscale defects in the cell membrane. IRE is not dependent on thermal energy and is therefore causing minimum damage to the blood vessels, nerves and tissue architecture. The present is a randomized, controlled trial, with a main purpose of looking into the safety and feasibility of irreversible electroporation for patients with benign prostatic obstruction.

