### **Description of Two Groups**

IRE group

Oral medication group

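### The only adverse-event outcome counts effects judged related to the procedure or the medication, so a between-arm safety comparison on it could be biased in an unknown direction

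*Protocol*

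**What the plan says.** Secondary Outcomes, item 6, is "The documentation of IRE procedure and medication related side effects". Its timing follows directly: "medication related side effects. Measured at baseline and 1, 3, 6 months during follow-up". No other outcome records adverse events. The primary outcome is change in maximum flow rate, and secondary items 1 to 5 are IPSS, IIEF, detrusor pressure at maximum flow, post void residual and prostate volume.

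Two of those bear on safety without any relatedness condition. For IIEF the protocol says "Measured using a standard IIEF scoring system", and for bladder emptying "post void residual volume (ml) will be measured via ultrasound". They cover sexual function and emptying only.

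The title frames the trial as "The safety and efficacy of irreversible electroporation versus standard medication". The Aims section, the Brief Summary and the Detailed Description all make the safety and feasibility of IRE the purpose of the study. The arms are given as labels: an IRE group and an "Oral medication group".

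**The concern.** An outcome restricted to related effects has a causal judgement built into it, and that judgement is made after treatment has been given. Randomisation balances the patients but not the judgement. Here the judgement is also not the same task in the two arms. An effect of the IRE procedure can be recorded only in a man who had the procedure, whereas in the medication arm the question is whether a drug caused the event.

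If the same complaint is attributed to treatment more readily in one arm than in the other, the recorded frequencies will differ for that reason alone. At stake is the safety comparison that the title announces. If events judged unrelated are also left off the form, no later analysis plan could restore them. If they are on the form, it could.

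**Working it through.** The protocol states no event rate, relatedness criterion or safety margin, so there is no figure to reproduce. The check is a reading of the text, plus one line of algebra showing why no size can be given.

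**1. Is item 6 the only adverse-event outcome?** Yes. Of the seven outcomes (one primary, six secondary), six are a flow rate, a symptom or function score, a pressure or a volume. Only item 6 records side effects.

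**2. Does the wording restrict what counts?** Yes. The effects are qualified as related to the procedure or to medication. The document does not say who judges this or by what criteria.

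**3. Is a between-arm comparison the intended use?** It is not stated. Items 1 to 5 are changes in a measured quantity, while item 6 is a documentation. But the trial is randomised, its title sets safety against standard medication, and safety is the main purpose. Comparison is therefore the natural use, though not a specified one.

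**4. Does the baseline measurement show what is collected?** No. At least three readings are open:
- a general check of symptoms or events in all men at every visit, in which the baseline entry is the pre-treatment state;
- related effects only, in which case a baseline entry has little meaning for trial treatment, since nothing can yet be related to it;
- side effects of medication a man is already taking. The Exclusion Criteria do not bar current drug treatment, and the Detailed Description calls oral drugs the mainstay.

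The word *related* favours a restricted outcome. The baseline visit fits the first or third reading better than the second. Nothing in the text decides between them.

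**5. What would a related-only count do to a comparison?** For an arm, let p be the proportion of men with an event of any cause, and s the share of those men whose event is judged related. Then

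recorded proportion = p × s,

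recorded risk ratio (IRE to medication) = (p_IRE / p_med) × (s_IRE / s_med).

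The second factor equals 1 only if the shares are equal. Shares can differ because the treatments truly cause different fractions of events, or because the judgement is applied differently to a procedure and to a drug. A record of related effects alone cannot separate the two. The protocol gives no value for p or s in either arm, so neither the sign nor the size of any distortion can be derived. If all events are counted in both arms, s = 1 in each and the factor disappears.

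**The case against.** The strongest reply is that harm needs several conditions at once, none of them shown: that item 6 is applied as a related-only outcome, that the arms are compared on it, and that attribution differs between them. For the loss to be beyond repair, unrelated events must also go uncollected. The document is a short synopsis, and the wording of one outcome in it is weak evidence of what the case report form holds. A descriptive record of procedural and drug effects could serve the stated aim, and the method of any safety comparison may properly sit in the analysis plan. All of this stands, and it limits the point to a possible bias. It does not remove the point: which events make up the outcome is protocol content, and as written the outcome depends on the attribution judgement.

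Three stronger conclusions are tempting and are not supported.
- *Unrelated events are not collected.* The text is silent on this, and the baseline visit leaves broader recording possible.
- *The bias favours IRE.* A reader might infer this because the Detailed Description describes IRE as "causing minimum damage to the blood vessels, nerves and tissue architecture" and says of drugs that "some patients can not tolerate long-term use, due to either side effects or limited efficacy". The first is background on mechanism. The second concerns long-term use and names limited efficacy alongside side effects. Events soon after a procedure might just as easily be attributed to it. These sentences support neither direction.
- *The bias has a given size.* Any number put into the formula would rest on invented shares.

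**Conclusion.** The point holds as a weakness in how the outcome is defined. The sole adverse-event outcome depends on a relatedness judgement whose target differs between a procedure arm and an oral-drug arm. A comparison of the arms on it could therefore be biased, in an unknown direction and by an unknown amount. No bias is shown for this trial.

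The conclusion assumes that item 6 is applied as worded and that the arms will be compared on it, which the title makes natural but no passage specifies. It does not assume that unrelated events go unrecorded. If they are recorded, an all-cause analysis remains possible and only the stated outcome needs changing. The change is a cheap improvement that should be made; confidence is medium because the wording leaves more than one reading open.

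**What to change.** Reword item 6 along these lines: *All adverse events, whatever the cause, recorded in the same way in both arms from randomisation to month 6, with relatedness to treatment as a separate field.* State that the baseline entry records pre-existing symptoms and any side effects of medication already being taken. Make the all-cause record the basis of any between-arm safety comparison, and report relatedness descriptively. Related effects can still be tabulated, so nothing now planned is lost.

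The cost is a change of protocol wording, a longer form and more data entry, with no added visits or procedures. The change removes the attribution step only. The protocol describes no blinding, and if one arm reports events more readily than the other, that difference would remain in the all-cause record.
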